5.2 Study Device and Use

5.2.1 Device Description

The EmitBio™ RD19 Device has been designed for ease of assembly in mass production and is comprised of the following three primary building blocks:

Aluminum Housing – The aluminum housing has been engineered for function and designed for ergonomics. The housing contains the LED metal core printed circuit board, the electronic LED power management circuit, an on/off switch interlocked with a timer, a rechargeable battery, and a removable cap for battery access. Dynamic modeling has been utilized to improve the dissipation of excess heat from the LED array by the housing to keep the RD19 within safe operating temperature limits. Incorporating a right angle, the housing also provides an ergonomic transition from the light source to the light delivery assembly as well as for single-handed use.

Light source - Located inside of the aluminum housing, the light source consists of an array of LEDs on a metal core circuit board, an electronic LED power management circuit, and a rechargeable battery. The quantity and characteristics (e.g. optical power and wavelength) of the individual LEDs in the LED array have been chosen to promote light-stimulated release and upregulation of nitric oxide. The focused zoom assembly has been engineered to improve homogenization of the light emitted from the LED array, transmit the pre-shaped beam into the oral cavity to a position approximately 9 cm from the target area, and to disperse the transmitted light over the target area for stimulation of the host tissue.

Mouthpiece – A comfort shield made of biomedical grade plastic is applied to the exterior of the optical element to enhance oral comfort during use and to improve light delivery. The positioning guard provides for repeatable placement of the RD-19 device while also preventing over insertion and preventing the lips from coming into contact with the aluminum housing. While the RD-19 device is in use, the mouthpiece is fixed to the aluminum housing and the tongue rests beneath the extended tongue depressor. When not in use, the assembly is removable for cleaning and, if necessary, replacement.

Each of the building blocks described are designed to allow the assembled device to meet specific criteria based on targeted safety and efficacy. The key target product device characteristics are summarized in:

Table 4: RD19 Device Characteristics

| Characteristic | Target |
|--------------------------------------|--|
| Route of Administration | Oral Illumination |
| Device Configuration | Hand-held, rechargeable |
| Blue Light Source | Non-coherent, light emitting diode (LED) array |
| UVA Content (315 nm – 400 nm) | <1% |
| UVB Content (280 nm - 315 nm) | not detectable* |
| UVC Content (100 nm - 280 nm) | not detectable* |
| Target Exposure Area | Oropharynx and surrounding tissues |
| Exposure Time | 3 min per treatment, 2X/day at least 4 hrs apart |
| Single Light Dose (@ 90 mm) | ~ 9 J/cm ² Joules = Watts x seconds |
| Total Daily Dose (@ 90 mm) | ~ 18 J/cm ² |
| Depth of Tissue Penetration | < 0.5 mm |
| Temperature (IEC 60601-1) | < 48 °C (for durations <10 min) |

*UVA/UVB not detectable in Labsphere 1M Integrating Sphere equipped with CDS-610 Mini CCD Array Spectrometer

5.2.2 Selection of Study Dose

In repeated experiments, including experiments conducted by external academic collaborators, it has been determined that the EmitBio™ RD19 device provides for a powerful reduction in viral infectivity of host cells after a single five (3) minute illumination at a modest energy level of 9 Joules/cm². SARS-CoV-2 virus infectivity is inhibited by 99% (approximately 2 logs) at this dose. Viral replication is inhibited by 99.9% (3 logs). Dosing twice a day allows NO levels to be elevated to an extent and for a time period expected to result in a high level anti-viral effect.

5.3 Use / Storage & Maintenance / Accountability

5.3.1 Acquisition and Accountability

The sponsor will provide 27 RD19 (25 volunteers with two reserves) devices packaged in appropriately labelled separate clear containers containing all components as well as instructions for use by study participants. Each RD19 device will be stamped on its power unit with a serial number. Study staff will ensure that each device's serial number is assigned to a specific study subject and the link between device serial number and study subject study number will be maintained on an accountability log. Subjects will be requested to bring their device to the clinic for each scheduled visit and study staff will confirm serial number and subject number are in concordance. Upon termination of a subject's participation in the trial, all RD19 devices and components must be returned to the study site and then to the study sponsor.

5.3.2 Device Appearance

RD19 Handle: ~6in.; Optic: ~3in.

5.3.3 Device Storage and Maintenance

All RD19 devices will be stored in a locked device storage room at the clinical trial site until needed for assignment to an enrolled study volunteer. Upon acquisition by the study subject, devices should be stored in a dry climate-controlled environment in the original plastic container in which it was provided. The device should be stored securely out of the reach of children who may mistakenly misuse the device, especially illumination of eyes – which is always to be avoided. The mouthpiece of the device is removable for rinsing with mild soap and warm water. The device tongue depressor and power housing may be cleaned with a soft cloth that has been dampened in mild dish detergent diluted in water; pieces should then be dried with a soft cloth. The optic device can be wiped gently with a dry cloth suitable for cleaning optical glasses.

5.3.4 Preparation for Use and Use

[Refer to **Appendix 1: User Instructions**]

5.5 Device Discontinuation

5.5.1 Study Pausing Criteria

RD19-01-3Q20 will be paused if any of the following events occur:

- Any subject experiences an SAE after use of the RD19 Device that is considered related to RD19.
- Any subject experiences laryngospasm, bronchospasm or anaphylaxis within 2 hours after use of the RD19 Device that is considered related to RD19.
- Two (2) or more subjects experience an allergic reaction such as generalized urticaria (defined as occurring at three or more body parts) within 72 hours after administration of light that is considered related to RD19.
- Three (3) or more subjects experience a \geq Grade 3 AE (systemic and/or clinical laboratory abnormality), in the same SOC grouping of Preferred Terms based on the Medical Dictionary for Regulatory Activities (MedDRA) coding, considered to be related to RD19.

Study device use and enrollments may resume only after review of the AEs that caused the pause results.

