1.1.4 Study Key Characteristics

Study Phase

- I

Study Population

- Twenty-five (25) males and non-pregnant females, 18 to 45 years of age, inclusive, who are in good health and meet all eligibility criteria will be enrolled.

Sites

- Carolina Phase I, Raleigh, NC

RD19 Device

- The EmitBio™ RD19 device emits visible blue light to stimulate host defenses (as explained below) and eliminate invading pathogens in the oropharynx and surrounding tissues. The RD19 device does this without additional photosensitizers or chemical reagents that are typically employed with traditional photodynamic therapies. Specifically, selected wavelengths of light have been evaluated across the visible spectrum, and it was discovered that a narrow wavelength band blue light emitted from non-coherent LED sources could perform both of the following functions: upregulate the sustained production of nitric oxide in epithelial tissue through the increase of NO synthases (NOSs); and stimulate the instantaneous release of the body's bound stores of nitric oxide. Nitric oxide also induces and recruits effector cells of the innate immune system, including natural killer (NK) cells, neutrophils and macrophages to phagocytize virus-infected cells at the site of primary infection.

Table 2: Treatment Group

| Group | RD19 | Duration |
|-------|------|------------|
| OL | 25 | 3' x 2/day |

Study Duration

- The duration of the entire study is anticipated to be \leq 18 days (from start of screening to last subject last visit).

Subject Duration

- The duration on trial for each individual subject is \leq 18 days (from start of screening to last visit).

Safety

- The study will use study pausing rules
- This study will involve the Sponsor's Chief Medical Officer as medical monitor, who along with the study PI(s) will assess severe AEs and SAEs, and together will constitute the attribution team.

1.2 Schedule of Activities (SOA) - Table 3

| Study Procedures | Screening Visit | Preliminary Observation | Full Assessment Period | |
|------------------------------------|-----------------|---|---|---|
| Study Day | ≤ -7 to 0 | 1 | 7 | Day 14/ Early Term |
| Study Procedures | | | | |
| Informed Consent | X | | | |
| Inclusion/Exclusion Criteria | X | X | | |
| Demographics Questionnaire | X | | | |
| Medical History | X | * Changes since last visit only | *Changes since last visit only | *Changes since last visit only |

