6.2.5 Definition of a Serious Adverse Event (SAE)

An SAE is defined in 21 CFR 312.32 as follows: “An AE is considered serious if, in the view of either the participating clinical site PI or appropriate sub-investigator or the sponsor, it results in any of the following outcomes:

- Death,
- A life-threatening AE,

- Inpatient hospitalization or prolongation of existing hospitalization,
- A persistent or significant incapacity or substantial disruption of the ability to conduct normal life functions,
- Or a congenital anomaly/birth defect.

Important medical events that may not result in death, are not immediately life-threatening, or require hospitalization may be considered serious when, based upon appropriate medical judgment, they may jeopardize the patient or subject and may require medical or surgical intervention to prevent one of the outcomes listed in this definition. An example of such a medical event would be an allergic bronchospasm requiring intensive treatment in an emergency room or at home to prevent the development of one of the definitions above.

“Life-threatening” refers to an AE that at occurrence represents an immediate risk of death to a subject. An event that may cause death if it occurs in a more severe form is not considered life-threatening. Similarly, a hospital admission for an elective procedure is not considered an SAE.

All SAEs, as with any AE, will be assessed for severity and relationship to study intervention. All SAEs will be recorded on the appropriate SAE e-CRF.

All SAEs will be followed through resolution or stabilization by a study clinician, licensed to make medical diagnoses and listed as the participating clinical site PI or appropriate sub-investigator.

All SAEs will be reviewed and evaluated by the Sponsor and will be reported to the IRB. This report will include severity, association with the study device, action(s) taken, and outcome.

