6.2.6 Serious Adverse Event Reporting

Any AE that meets a protocol-defined criterion as an SAE must be submitted immediately (within 24 hours of site awareness) on an SAE form to EmitBio Inc. Pharmacovigilance:

EmitBio™ Pharmacovigilance

SAE Hot Line: [name] or [name]

Text Immediate Report: [name]

SAE Email: [contact]

In addition to the SAE form, all SAE data must be entered into the SAE e-CRF.

Other supporting documentation of the event may be requested by EmitBio™ Pharmacovigilance and should be provided as soon as possible. The Sponsor Medical Monitor will review and assess the SAE for regulatory reporting and potential impact on study subject safety and protocol conduct.

At any time after completion of the study, if the participating clinical site PI or appropriate sub-investigator becomes aware of an SAE that is suspected to be related to study product, the participating clinical site PI or appropriate sub-investigator will report the event to the EmitBio™ Pharmacovigilance Group.

Regulatory Reporting of Device-related SAEs

Following notification from the participating clinical site PI or appropriate sub-investigator, EmitBio Inc., as the sponsor, will report to the FDA and will copy the clinical site investigators on all reports of potential serious risks from clinical studies of RD19, as soon as possible. EmitBio Inc. will report to the FDA any unexpected fatal or life-threatening suspected adverse reaction as soon as possible, but in no case later than 7 calendar days after the sponsor's initial receipt of the information. If the event is not fatal or life-threatening, an SAE safety report will be submitted within 15 calendar days after the sponsor determines that the information qualifies for reporting as specified in 21 CFR Part 312.32.

Relevant follow-up information to the safety report will be submitted as soon as the information is available. Upon request from FDA, EmitBio™ will submit to the FDA any additional data or information that the agency deems necessary, as soon as possible, but in no case later than 15 calendar days after receiving the request.

SAEs that are not considered related to RD19 will not be reported to the FDA.

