6.2.9 Relationship to Study Intervention

For each reported adverse event, the participating clinical site PI or qualified designee must assess the relationship of the event to the study device using the following guidelines:

- Related – The AE is known to occur with the study intervention, there is a reasonable possibility that the study intervention caused the AE, or there is a close temporal relationship between the study intervention and event. Reasonable possibility means that there is evidence to suggest a causal relationship between the study intervention and the AE.
- Null Determination – The direction and magnitude towards related and not related is null. The investigator is stating simply, “I cannot determine a relationship”.
- Not Related – There is not a reasonable possibility that the administration of the study intervention caused the event, there is no temporal relationship between the study intervention and event onset, or an alternate etiology has been established.

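### All four pausing criteria in 5.5.1 count only related events, so a Null Determination triggers no mandatory pause; the practical gap is mainly SAEs (criterion 1) and same-SOC Grade 3 clusters (criterion 4)

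*Combined protocol and SAP*

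**What the plan says.** Section 5.5.1 has four criteria, any one of which pauses the study:

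1. One SAE: "Any subject experiences an SAE after use of the RD19 Device that is considered related to RD19".
2. One acute airway event or anaphylaxis in the two hours following use, with the same relatedness condition.
3. Two or more subjects with an allergic reaction within 72 hours of illumination, again only if related.
4. Three or more subjects with an AE of Grade 3 or higher in the same system organ class (SOC), "based on the Medical Dictionary for Regulatory Activities (MedDRA) coding, considered to be related to RD19".

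After a pause, "Study device use and enrollments may resume only after review of the AEs that caused the pause results".

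Section 6.2.9 defines Related, Null Determination and Not Related as separate categories. On Null Determination it says "The direction and magnitude towards related and not related is null". Related is broad. One of its alternative grounds is "or there is a close temporal relationship between the study intervention and event".

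Other provisions apply outside the pausing rule. Under 1.1.4 the sponsor's Chief Medical Officer, as medical monitor, and the PI(s) "will assess severe AEs and SAEs, and together will constitute the attribution team". Section 6.2.6 requires SAEs to reach the sponsor within 24 hours and adds: "The Sponsor Medical Monitor will review and assess the SAE for regulatory reporting and potential impact on study subject safety and protocol conduct". Section 6.2.5 states: "All SAEs will be reviewed and evaluated by the Sponsor and will be reported to the IRB". Section 5.5.3 lists an SAE, whatever its attribution, as a reason to remove that subject.

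**The concern.** The protocol creates a third attribution category and then writes its pausing rule as if there were only two. On the plain wording, an honest statement that causality cannot be determined has the same effect on the pause as a finding of Not Related.

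That answer is foreseeable here. The device has not been used in people before, and section 7.2 confirms that there is no placebo arm to show the background rate. Section 4 expects the last Day 1 visit within about a week of the start of enrollment, so most subjects will be using the device at the same time. What is at stake is whether use must stop for review after an SAE that nobody can attribute, or after three severe events in one SOC of which one is rated Null.

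**Working it through.** **Text check.** The four criteria in 5.5.1 were set against the three categories in 6.2.9. All four require relatedness. None is independent of attribution, and no available section says how Null counts. The contents list names a section on subject pausing criteria and one on unanticipated problems, but neither appears in the body as supplied. The statement is therefore limited to the available text.

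**Which criteria are exposed.** Use is twice daily, at least 4 hours and ideally 8 to 12 hours apart (3.1), and AEs are reported from Day 1 use through Day 14 (6.2.1).

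- Criterion 2 has a two-hour window, so a qualifying event is close in time to use almost by definition and should be rated Related.
- Methemoglobin is measured before and 60 minutes after use in the clinic (Table 3), so a post-use rise is also close in time.
- Criterion 3 also has a time window, though a longer one.
- Criteria 1 and 4 have no window. An SAE or a Grade 3 event may have an onset or cause that the assessor cannot place.

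**Illustration of a miss.** The plan gives no operating characteristics for the pausing rule, so there is no figure to reproduce. Let *u* be the share of qualifying events rated Null (assumed).

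- Criterion 1, one qualifying SAE: P(miss) = *u*.
- Criterion 4, exactly three qualifying subjects with independent ratings: P(miss) = 1 − (1 − *u*)³.
- Criterion 4, if the three ratings move together: P(miss) = *u*.

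| Assumed *u* | Criterion 1 | Criterion 4, independent | Criterion 4, together |
|---|---|---|---|
| 10% | 10% | 1 − 0.90³ = 27.1% | 10% |
| 25% | 25% | 1 − 0.75³ = 57.8% | 25% |
| 50% | 50% | 1 − 0.50³ = 87.5% | 50% |

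With 25 subjects and an assumed true Grade 3 risk *p* in one SOC, P(criterion 4 met) = P(Bin(25, *p*(1 − *u*)) ≥ 3), ratings independent. At *p* = 20% and *u* = 0 this is 1 − (0.0038 + 0.0236 + 0.0708) = 90.2%.

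| *p* | *u* = 0 (Null counted) | 10% | 25% | 50% |
|---|---|---|---|---|
| 20% | 90.2% | 85.3% | 74.6% | 46.3% |
| 5% | 12.7% | 10.0% | 6.6% | 2.4% |

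**Extra pauses if Null counts.** First, upper bounds that treat every background event as Related or Null, with assumed background rates:

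- Criterion 1: 1 − (1 − *p*)²⁵ = 2.5% at 0.1% and 11.8% at 0.5%.
- Criterion 3: P(Bin(25, *p*) ≥ 2) = 0.03% at 0.1% and 0.7% at 0.5%.
- Criterion 4: P(Bin(25, *p*) ≥ 3) = 0.2% per SOC at 1% and 1.3% at 2%. Over ten independent SOCs, 1 − (1 − *q*)¹⁰, with *q* the per-SOC value, is 1.9% to 12.5%.
- Criteria 1 and 4 together, taken as independent: 4.4% to 22.8%.

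The change itself costs less, because Related events already pause the study and Not Related events still would not. For criterion 1 with *u* = 25%, the addition is at most 1 − (1 − 0.25*p*)²⁵. That is 1 − 0.99975²⁵ = 0.6% at *p* = 0.1%, and 1 − 0.99875²⁵ = 3.1% at *p* = 0.5%.

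**The case against.** The strongest reply is that Null will seldom be used. A close temporal relationship is enough for Related, and with twice-daily use nearly every reportable event in a compliant subject begins within hours of an illumination. This largely settles criterion 2 and post-use methemoglobin. It does not settle criteria 1 and 4. Section 6.2.9 does not say how close is close, and it still offers Null as a valid answer. If assessors always apply the temporal ground, Null stays empty and the change costs almost nothing. If they do not, the gap is real.

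A second reply is that an unattributable SAE is not ignored. It reaches the sponsor within 24 hours, the medical monitor weighs its effect on safety and conduct, the IRB is told, and the subject may be removed. Subjects must also contact the site at once about any AE of more than moderate intensity (3.1). This stands. A reader might infer that a Null event cannot pause the study at all. The documents do not support that, because 5.5.1 lists mandatory triggers and nothing forbids a discretionary pause. What is missing is the obligation. The SAE review also does not cover criterion 4 events that are not serious.

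A third reply is that the percentages rest on little. This also stands. One attribution team rating three similar events is unlikely to rate them independently, and a cluster may itself move a rating from Null to Related. A 20% Grade 3 rate fits poorly with a protocol that expects mild local reactions (2.2.1). At 5%, criterion 4 is met only 12.7% of the time even with Null counted, so the three-subject threshold limits it far more than the Null category does.

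**Conclusion.** The point holds as a reading of the text: one of the three permitted attributions has no stated consequence under the pausing rule, and a Null event triggers no mandatory pause. It matters mainly for criteria 1 and 4. A reader might infer that all four criteria are equally exposed, but the definition of Related in 6.2.9 and the two-hour window in criterion 2 argue against that.

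A reader might also take the tabulated miss probabilities as the size of the problem. They are not. The Null shares and event rates are assumptions, and the higher criterion 4 figures also need independent ratings. If the ratings move together, the miss probability is simply the Null share. The conclusion rests on the wording and does not need these figures.

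**What to change.** In 5.5.1, replace the relatedness condition that closes each of the four criteria with: *assessed as Related or Null Determination (6.2.9)*. No other text needs to change.

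This adds no visit, sample or subject. The price is an occasional extra pause, with a review before use may resume. A pause is not trivial here. It interrupts a 14-day regimen in a study planned to last at most 18 days, subjects who have used the device are not replaced (5.5.3), and the per-protocol population requires compliance with all procedures to Day 14 (7.3), so that population may shrink. For criterion 1 the added chance of a pause is at most about 0.6% to 3.1% under the assumptions shown. No figure is offered for criterion 2, where few events should be rated Null. For a first-in-man study this is a reasonable price for a rule that covers every attribution the protocol allows.

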5.5.2 Subject Elects to Discontinue

A study volunteer may elect to discontinue participation in the trial at any time. Investigative staff will ask the volunteer to return for an early termination, but they are under no obligation to do so. All study subjects must return the RD19 device at study termination.

5.5.3 Investigator Decision to Discontinue Subject Use of Device

A subject may be removed from the study for the following reasons post initial device use; however, whenever possible the subject should be followed for safety evaluations per protocol:

- Study non-compliance to protocol requirements that in the opinion of the participating clinical site PI or appropriate sub-investigator poses an increased risk (e.g., missing safety labs) or compromises the validity of the data.

- Lost to follow-up. (*A subject will be considered lost to follow-up if he or she fails to appear for a follow-up assessment. Extensive effort (i.e., generally three documented contact attempts via telephone calls, e-mail, etc., made on separate occasions) will be made to locate or recall the subject, or at least to determine the subject's health status. These efforts will be documented in the subject's study file.*)
- Medical disease or condition, or new clinical finding(s) for which continued participation, in the opinion of the participating clinical site PI or appropriate sub-investigator, might compromise the safety of the subject, interfere with the subject's successful completion of this study, or interfere with the evaluation of safety.
- If any AE, clinical laboratory abnormality or situation occurs such that continued participation in the study would not be in the best interest of the subject.
- The occurrence of a SAE.
- If the subject is using the device in any manner inconsistent with instructions and protocol directives and procedures.

If the subject agrees, every attempt will be made to follow all AEs through resolution or stabilization.

Subjects who withdraw, or are withdrawn from this study, or are lost to follow-up after signing the informed consent form (ICF) and use of the RD19 device will not be replaced. Subjects who withdraw, or are withdrawn from this study, or are lost to follow-up after signing the ICF but before use of the device may be replaced.

The reason for subject discontinuation or withdrawal from the study will be recorded on the appropriate e-CRF.

